1.4 Abbreviations and definitions

SAP: Statistical Analysis Plan

STR: Swiss Trauma Registry

MT: Massive Transfusion

ISS: Injury Severity Score

AIS: Abbreviated Injured Scale

SBP: Systolic Blood Pressure

ABC: Assessment of Blood Consumption

GCS: Glasgow Coma Scale

RBC: Red Blood Cell

FFP: Fresh Frozen Plasma

FAST: Focus Assessment with Sonography Trauma

TBI: traumatic brain Injury

BATT: Bleeding Audit and Triage Trauma Score.

CPR: Cardiopulmonary reanimation

TASH : Trauma-Associated Severe Haemorrhage

2. Introduction

2.1 Background and rationale

Since the 2000s, many prognostic scores were developed to predict traumatic haemorrhage. Most of these studies were retrospectives based on registers. Due to missing data on death due to bleeding, these studies chose to predict the massive transfusion risk as a surrogate of haemorrhagic death. These scores include clinical parameters (vital signs), laboratory values (Haemoglobin, lactate, Base excess) and/or imaging (CT or ultrasound) values. The scores showing best performance are the Trauma Associated Severe Haemorrhage (TASH) score, developed and validated on the German register (DGU-Register) (1, 2) and the ABC score developed and validated in the United States of America (3, 4). The scores with variables are described on Figure 1,2.

However, the majority of these scores cannot be applied at the trauma scene due to the unavailability of laboratory and imaging values. Therefore, their clinical utility remains unclear. To overcome the need for diagnostic tests, authors have developed and recently validated a clinical prognostic score in identifying trauma patients with, or at risk of, significant haemorrhage based on predicted probabilities of death due to bleeding: BATT score (5). This score was developed from an international cohort using data from 271 Trauma Centres in 41 countries on 5 continents and uses first clinical parameters at initial assessment. The BATT score predicts death due to bleeding and has been validated on a large population in England and Wales. It could also predict massive transfusion, as a surrogate of haemorrhagic death, earlier at the trauma scene. Its feasibility and external validation would make its clinical utility superior to other scores while identifying a greater number of patients requiring early management.

Our study is an external validation of pre-existing prognostic scores of traumatic haemorrhages (TASH^{1,2}, ABC^{3,4} and BATT⁵ score) at different times of care (Scene of Injury, admission at the trauma room) in order to assess their overall performance, discrimination and calibration in the prediction of massive transfusion, and haemorrhagic death. The objective of the study is to assess a comparison of score performances (Overall performance, discrimination and calibration).

3. Study Methods

3.1 Study Design

The MTP STUDY is a retrospective, observational, non-interventional study based on a multicentric, anonymised Register. The Study is conducted by the emergency department of the University Hospital (CHUV) in Lausanne, Switzerland. The study design is observational, and no intervention is applied as part of the study protocol.

The SAP of this study will be registered at www.clinicaltrials.gov.

3.2 Sample Size and Power consideration

As his study is retrospective, the sample size is fixed. The number of participants will depend on the STR Database. The investigators anticipate using the data of 10'000 participants included in the Swiss Trauma Registry from 1st January 2015 to 31st December 2019. A post-hoc power calculation will be performed.

3.3 Timing of Final analysis

This statistical plan will be added to the study protocol at www.clinicaltrials.gov, after receiving the STR approval. It will be added before receiving the dataset and before any analyses have been conducted.

After receiving the dataset, the investigators will check for data consistency. Once the database has been checked, statistical analysis will be performed (October 2020)

3.4 Ethical Approval

As is mandatory in Swiss law (KVG), STR is authorised **by the Human Research Act (HRA)** as a quality registry for the Highly Specialised Medicine (HSM). Due to the retrospective aspect of our observational study based on an anonymized registry (identity, date of birth, trauma scene and hospital location unknown) and according to the swiss law by the HRA (Art. 2), the investigators don't need a protocol submission to an ethics committee.

4. Study Population

4.1 Screening Data

The investigators will use data from the Swiss Trauma Registry (STR)⁶, which represents the Swiss trauma system, serving the country's 8.6 million inhabitants. The STR collect data on patients with major trauma who have been admitted to a level I Swiss trauma centre (Centre Hospitalier Universitaire Vaudois, Hôpitaux universitaires Genevois, Inselspital Bern, Universitätsspital Basel, Universitätsspital Zürich, Kantonsspital St. Gallen, Luzerner Kantonsspital, Kantonsspital Aarau, Kantonsspital Graubünden, Kantonsspital Winterthur, EOC – Ospedale Regionale di Lugano, Gesundheitsnetzwerk Wallis – Standort Sion). Major trauma has been defined according to the inclusion criteria of the STR.

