
Objective(s):
	
 - External validation of pre-existing prognostic scores of traumatic haemorrhages at different times of care (Scene of Injury, admission at the trauma room) in order to assess their overall performance, discrimination and calibration in the prediction of massive transfusion and haemorrhagic death. - Comparison of score performances (Overall performance, discrimination and calibration).

Outcome(s):
	
Primary study outcome :
 
 - Massive transfusion defined by a transfusion equal to or greater than 10 Red blood cell (RBC) / 24 hours or ≥ 3 RBC in the first hour if available in the Swiss Trauma Registry. 
Secondary study outcome :
 
 - Death due to bleeding (if available in the registry) - Early death (< 24 hours) - Coagulopathy at admission defined by INR > 1.2, quick TP < 70% or Fibrinogen < 1.5 g/L (6,7,8)

Study design:
	
Observational non-interventional study based on a multicentric anonymized registry

Inclusion / Exclusion criteria:	
Study population: All adult trauma patients treated at twelve Swiss trauma centres Level I from 01.01.2015 to 31.12.2019 with eligible criteria of the Swiss Trauma Registry (STR) are included. All data from the register are anonymised without any access to medical files. The identity of the trauma patients, date of birth, address and trauma scene location are unknown (as mandatory by the swiss law: Art. 2 ORH).
 
Inclusion criteria:
 
- Age > 16 years old- ISS (Injury Severity Score) ≥ 16 and/or AIS head (Abbreviated Injured scale) ≥ 3 
Exclusion criteria:
 
- Age < 16 years old- ISS < 16 and or AIS < 3- Isolated Burns (including electric shock) or if the burn is clearly the primary injury- Patients arriving at the trauma room with no sign of life and no diagnostic/therapeutic measures have been initiated for them- Choking or hanging patient without any other injury.- Drowning patients
--	---

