4.2 Eligibility

All trauma patients included in the STR between 01.01.2015 and 31.12.2019 have been recorded according to these inclusion criteria of the STR⁶:

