4.3 Baseline patient characteristics

4.3.1 *Collected baseline patient characteristics*

The observational study is designed to record a set of demographical data, clinical examination in prehospital or in-hospital setting, in-hospital biochemical values and imaging variables for each included patient. The investigators will extract the data from the Swiss trauma registry (STR). The investigators plan to extract the biological parameters from the register at the trauma room stage. The clinical examinations will be the first measures at the pre and in-hospital stage. **Table 1** provides an overview of all variables requested from the registry before receiving the dataset.

4.3.2 *Descriptive summary of baseline patient characteristics*

The investigators will list general patient characteristics in a baseline characteristics table. Data will be presented as mean with standard deviation (SD) when normally distributed or as median with interquartile range in case of skewed data. Dichotomous and categorical data will be presented in proportions. **Table 2** provides a summary of potential baseline characteristics.

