5.2.1. Imputation method

To estimate baseline risk for the full dataset, the investigators will replace missing predictors using multiple imputation by chained equations on sex, age, systolic blood pressure, respiratory rate, heart rate, Glasgow coma scale, Haemoglobin, base excess, type of injury (penetrating/blunt) Instable pelvis fracture and open/dislocated femur fracture with 20 imputed dataset. All analysis and results will be present in two subgroups: missing data imputed and missing data excluded.

5.2.2. Early deaths and early deaths with haemorrhage as a proxy for death due to bleeding

Because the investigators don't know if the Swiss Trauma Registry record the cause of death, the investigators expect some missing data about death due to bleeding as a secondary outcome. In case of missing data on secondary outcomes, the investigators will use early deaths and early deaths with evidence of haemorrhage as a proxy for death due to bleeding. Specifically, the investigators will included deaths from all causes within 12 hours of injury (excluding massive destruction of skull or brain; asphyxia, drowning and hanging are already excluded from the STR) and deaths between 12 to 24 hours with evidence of bleeding (Activation of massive transfusion protocol or blood within 6 hours or an abbreviated injury scale (AIS) diagnosis associated with haemorrhage: Blood loss >20%, Aorta [OR] Vena Cava [OR]carotid [OR]femoral [OR]Major arteries [OR]veins AND laceration, - Spleen [OR]liver [OR] Kidney [OR] Myocardium [AND] major laceration, major haemothorax, retroperitoneum haemorrhage).

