5.4 Statistical Software

All analyses will be performed using STATA software (version 16.0; Stata Corp, College Station, TX, USA).

6. Discussion

Due to the study population (STR), which is partly integrated into the German DGU-Register, the investigators expect good transportability of the TASH score to the Swiss Trauma Registry in terms of overall performance, discrimination and calibration. The ABC score should show lowers results in terms of discrimination due to its validation on small cohorts exclusively in North America. The new BATT score predicting death due to bleeding has been validated on a large English cohort of more than 100,000 patients. It identifies all patients with haemorrhage and not only patients who have received a massive transfusion subject to survival bias. In this context, the BATT score provides good discrimination with only simple physiological variables available at the trauma scene. In case of its external validation on the STR as part of our study, its feasibility would make its clinical utility superior to other pre-existing scores, while identifying a greater number of patients requiring early management. Its application would activate a massive transfusion plan directly at the trauma scene and save precious time.

7. Conclusion

This SAP presents the principles of analysis of the MTP study and discusses its major methodologic and statistical concerns. The investigators hope that the results of the MTP study will be as transparent and robust as possible, so that the investigators minimised the risk of outcome reporting bias and data-driven results.

8. Tables and Figures

Table 1. Overview of all variables requested from the STR for the MTP study.

Variable	Prehospital	In-hospital Trauma room	First 24 hours
Demographics			
Age	X		
Gender	X		
Type of accident	X		
Mechanism of Injury	X		
Accident date	X		
Accident time	X		
Medical past	X		
Arrival on scene (paramedics, date/time)	X		
Arrival on scene (medics, date/time)	X		
Physician Staffed Ambulance (yes/no)	X		
Hospital Arrival (date/time)		X	
Clinical examination (first measures recorded)			
Heart Rate	X	X	
Systolic blood pressure	X	X	
Respiratory rate	X	X	
Pulse oximetry	X	X	
Temperature	X	X	
Glasgow Coma Scale	X	X	
Cardiopulmonary Reanimation	X	X	
Biological parameters			
Haemoglobin		X	
Platelets		X	
Lactates		X	
TP		X	

INR		X	
PTT		X	
Fibrinogen		X	
Base excess		X	
Therapy			
Vasoactive drugs (doses, type)		X	
Tranexamic acid (doses, date/time)	X	X	

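### Eligibility sets no limit on the time from injury to arrival, so late arrivals can have imputed scene values and a partly or wholly elapsed window for the injury-anchored death proxy

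*SAP*

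**What the plan says.** The protocol synopsis takes as its population "All adult trauma patients treated at twelve Swiss trauma centres Level I from 01.01.2015 to 31.12.2019" who meet the registry's criteria. SAP 4.1 describes the source in similar terms: "The STR collect data on patients with major trauma who have been admitted to a level I Swiss trauma centre". SAP 4.2 states that the patients "have been recorded according to these inclusion criteria of the STR". The criteria listed there cover age, ISS or head AIS, burns, absence of signs of life, choking or hanging, and drowning. None concerns delay or earlier care at another hospital, and no subgroup in SAP 5.3 is defined by either.

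On predictors, SAP 4.3.1 says: "The clinical examinations will be the first measures at the pre and in-hospital stage". On missing values, SAP 5.2.1 (Imputation method) says: "To estimate baseline risk for the full dataset, the investigators will replace missing predictors using multiple imputation by chained equations". The variables it lists are demographic, physiological, laboratory and injury variables. It also promises every result with missing data excluded.

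On outcomes, the section on early deaths as a proxy for death due to bleeding counts "deaths from all causes within 12 hours of injury", with some exclusions, and then deaths at 12 to 24 hours with evidence of bleeding. The windows for massive transfusion and for early death in SAP 5.1 have no stated time origin.

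**The concern.** The study asks how the scores perform at the scene and at trauma-room admission. A patient who reaches the level I centre many hours after injury fits neither moment well, yet is fully eligible.

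Three things follow:

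- The first recorded trauma-room values may come after hours of earlier care.
- If scene values are missing, they are filled in by a model that knows neither the delay nor the outcome.
- Part or all of the injury-anchored proxy window has been survived before the patient could enter the registry, and the patient is then counted as a non-event.

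BATT is the most exposed. SAP 5.2.4 says that its calibration cannot be judged against massive transfusion and will be judged against death due to bleeding or early death. The SAP expects that cause of death may not be recorded, in which case the proxy takes over. A score that is well calibrated in promptly admitted patients could then appear to over-predict.

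**Working it through.** **The plan's own figure.** The only size stated is about 10,000 participants, fixed by the registry (SAP 3.2). It is a projection with no calculation behind it, so there is nothing to reproduce. It serves below only as a scale.

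**Step 1: how much of the proxy window remains at arrival.** I take both components to run from injury. The text says so for the first, and it is the natural reading for the second. With delay d in hours, the time left is max(0, 12 − d) for the first component and max(0, 24 − d) for the whole proxy.

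| Delay (h) | Left of 12 h | Left of 24 h |
|---|---|---|
| 1 | 11 | 23 |
| 6 | 6 | 18 |
| 12 | 0 | 12 |
| 24 or more | 0 | 0 |

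The first component is therefore impossible from 12 h, and the whole proxy from 24 h. Shorter delays shorten the window without closing it.

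**Step 2: effect on P/O.** Let f be the share of late arrivals, p the event risk in the others, and r the observed risk in late arrivals. Assume a score that is perfectly calibrated in the others and predicts p on average in late arrivals too. Then

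P/O = p / [(1 − f)p + f·r].

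With r = 0 this becomes 1/(1 − f), whatever p is. With r between 0 and p it lies between 1/(1 − f) and 1. The documents give no value for f, p or r; those below are assumptions.

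| f | Late patients of 10,000 | Overall event rate if p = 5% | P/O with r = 0 |
|---|---|---|---|
| 1% | 100 | 4.95% | 1/0.99 = 1.01 |
| 5% | 500 | 4.75% | 1/0.95 = 1.05 |
| 10% | 1,000 | 4.50% | 1/0.90 = 1.11 |

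**Step 3: effect on AUROC.** Let w be late arrivals divided by all non-events. The observed AUROC is (1 − w) × AUROC + w × AUROC_late, where AUROC_late is the score's ability to separate true events from late arrivals. For f = 5% and p = 5% there are 475 events, so w = 500/9,525 = 0.052. Take a true AUROC of 0.80.

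| f | AUROC_late = 0.5 | AUROC_late = 0.95 |
|---|---|---|
| 1% | 0.797 | 0.802 |
| 5% | 0.784 | 0.808 |
| 10% | 0.769 | 0.816 |

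The direction depends on how late arrivals score, so no direction can be asserted.

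**Step 4: is the remedy within reach?** Table 1 requests accident date and time and hospital arrival date and time, so delay can be derived. The SAP does not use it.

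**The case against.** The strongest reply is that the primary outcome is largely untouched. Massive transfusion has no stated time origin, and red cells are requested under the trauma-room column. A reader might infer that late arrivals are near-certain non-events throughout. The documents do not support that. Only the proxy is expressly tied to injury, and it is a fallback for one secondary outcome. Early death within 24 h has no stated origin; if it is counted from admission, late arrivals can have it.

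A reader might also infer that every late arrival receives imputed scene values. Only missing values are imputed, and nothing says that late arrivals lack scene records. Equal predicted risk is doubtful too: the imputation variables include haemoglobin, base excess and vital signs, so a stable late arrival need not be given an average risk.

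It is tempting as well to treat the six-hour blood criterion in the proxy as the SAP's own arrival limit. It is a marker of bleeding among deaths at 12 to 24 h and says nothing about arrival.

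Finally, the plan already has a complete-case analysis, and SAP 4.4 accepts that admission vital signs are altered by treatment during transport. Neither closes the gap. Complete-case analysis keeps late arrivals whose values are recorded, and SAP 4.4 discusses neither delay nor care at another hospital. The other limits stand and define the scope of the point.

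**Conclusion.** The gap is real but narrow. No limit on delay and no rule for patients first treated elsewhere appears in the text provided. Followed as written, patients who outlived part or all of the proxy window before arrival count as non-events. The event is impossible only from 12 h (first component) or 24 h (whole proxy).

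The likely consequence is an upward shift in P/O, chiefly for BATT against the proxy, and a shift in AUROC of unknown direction. The P/O figures of 1.01 to 1.11 rest on assumed late shares of 1% to 10%, no events among late arrivals and equal predicted risk. They are not estimates for this registry and do not carry over to massive transfusion. The true share could be negligible. The case for a change rests on how little it costs.

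**What to change.** In SAP 4.2 and in the outcome and missing-data parts of section 5:

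1. State the time origin of every outcome window: massive transfusion (24 h and first hour), early death, and both components of the proxy.
2. Derive delay as hospital arrival minus accident time, and report its distribution.
3. Exclude from the injury-anchored proxy analyses patients who arrive after the 24 h window has closed, and do not impute scene values for them.
4. Prespecify an analysis restricted to early arrivals, reported beside the full registry cohort. Fix the delay limit before the dataset is received, and justify it on its own grounds, not by the six-hour blood criterion.
5. Request transfer status under the protocol's provision for additional variables. If it is supplied, also report an analysis restricted to direct arrivals.

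The cost is some SAP wording, one derived variable and the additional restricted analyses. The restricted cohort will be somewhat smaller, and patients with a missing accident time will appear only in the full-cohort analysis. SAP 3.3 places registration of the plan before data receipt, which leaves room to settle this in advance.

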4.2 Eligibility

All trauma patients included in the STR between 01.01.2015 and 31.12.2019 have been recorded according to these inclusion criteria of the STR⁶:

4.2.1. Inclusion criteria

- Age > 16 years old
- ISS \geq 16 and/or AIS head \geq 3

4.2.2. Exclusion criteria

- Age < 16 years old
- ISS < 16 and/or AIS head < 3
- Isolated Burns (including electric shock) or if the burn is clearly the primary injury
- Patients arriving at the trauma room without signs of life and no diagnostic/therapeutic measures have been initiated for them
- Choking or Hanging patient without any other injury
- Drowning patients

4.3 Baseline patient characteristics

4.3.1 *Collected baseline patient characteristics*

The observational study is designed to record a set of demographical data, clinical examination in prehospital or in-hospital setting, in-hospital biochemical values and imaging variables for each included patient. The investigators will extract the data from the Swiss trauma registry (STR). The investigators plan to extract the biological parameters from the register at the trauma room stage. The clinical examinations will be the first measures at the pre and in-hospital stage. **Table 1** provides an overview of all variables requested from the registry before receiving the dataset.

4.3.2 *Descriptive summary of baseline patient characteristics*

The investigators will list general patient characteristics in a baseline characteristics table. Data will be presented as mean with standard deviation (SD) when normally distributed or as median with interquartile range in case of skewed data. Dichotomous and categorical data will be presented in proportions. **Table 2** provides a summary of potential baseline characteristics.

4.4 Assumed confounding covariate

The majority of the requested variables from the STR are inevitably correlated, as most relate to the haemodynamic status of the patient and the trauma severity. The values of the variables can be confounded by unmeasured factors, such as environmental, genetic or psychological influences. Therefore, the investigators provide an example of possible confounding variables:

- Clinical examinations in prehospital settings (i.e. heart rate, systolic blood pressure, respiratory rate, Glasgow Coma scale) are assumed to be confounded by:
 - Quality of the measurements, stress, pain and anxiety. These confounding covariates should be minor for the statistical analysis.
- Clinical examinations at hospital admission (i.e. vitals signs) are assumed to be confounded by:

- Quality of the measurements, administration of inotropes and/or vasopressors during transport, administration of propofol (negative inotropic effect), induced comas and the need for mechanical ventilation.
- Because some patients will not survive long enough to receive 10 red blood cell units, massive transfusion is subject to misclassification. To correct this misclassification, the investigators add in the massive transfusion definition the use of ≥ 3 RBC administered in the first hour (if the variable is available in the registry).
- The trauma-induced coagulopathy as secondary outcome is assumed to be confounded by anticoagulant treatments. To counteract the confounding covariate, the investigators will include the fibrinogen < 1.5 g/L in the definition of trauma-induced coagulopathy. The investigators will also define a subgroup of patients with anticoagulant treatment or not.

The investigators acknowledge that there will be residual confounding in our dataset due to the presence of unmeasured confounding, some of which is listed above. However, the actual measured variables reflect daily practice and so are assumed to reflect similar confounding in daily assessments.

5. Analysis

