
Measurements and procedures:
	
Predictive Variables:
 
Demographics: Age, gender, type of accident, mechanism of Injury (penetrating/blunt), Hospital (anonymised by number), Date and time of accident.
 
Prehospital settings: Arrival on scene (paramedics, date/time and medics, date/time), type of transport: physician staffed ambulance/helicopter, Firsts clinical measures recorded: Systolic blood pressure (SBP), Respiratory rate (RR), Heart Rate (HR), Pulse Oximetry, Glasgow coma scale, temperature, cardiopulmonary reanimation, Drugs Use: Tranexamic acid (Date/time) and vasoactive, early death before arriving to the hospital.
 
In-hospital settings (trauma room): Hospital arrival (date/hour), Firsts measures: Systolic blood pressure (SBP), Respiratory rate (RR), Heart Rate (HR), Pulse Oximetry, Glasgow coma scale, temperature, cardiopulmonary reanimation, Biological parameters: haemoglobin, Platelets, lactates, Base excess, TP (sec and %), INR, PTT, Fibrinogen, Drugs use: Tranexamic acid (date/time), vasoactive, Vitamin K, Fibrinogen, Prothrombin complex concentrate, rFVIIa, Red blood cell (number in the first hour, date/hour of each Red blood cell), platelets units, fresh frozen plasma.
 
Imaging: type of imaging, results: positive or negative for free fluid, date/time of imaging.
 
Diagnosis: AIS final, ISS final, Medical past, use of anticoagulant/antiaggregant before trauma
 
Outcome: Date/time of death, Early death (<12 hours), Early death (<24 hours), number of red blood cell in 24 hours, Massive transfusion (defined as ≥ 10 red blood cells in the first 24 hours).
 
Depending of the availability of requested variables in the registry, we will ask for complementary variables.
 
Comparison:
 
Performance comparison of pre-existing scores (TASH, ABC and BATT scores) in term of overall performance, discrimination and calibration.
 
Evaluation of clinical utility and feasibility in prehospital settings and emergency admission.

Intervention:
	
Comparison of score performances (Overall performance, discrimination and calibration)

Control Intervention (if applicable):
	
No group controls

Number of Participants with Rationale:
	
The number of participants will depend of the Swiss Trauma Registry Database. We project to include 10'000 participants for our study. A post-hoc power calculation will be performed.

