5.1 Outcome definitions

6.1.1 Primary outcome

The primary outcome is the presence of massive transfusion (MT) in Swiss trauma patients, defined by a transfusion equal to or greater than 10 Red blood cell (RBC) in the first 24 hours or ≥ 3 RBC in the first hour if available in the Swiss Trauma Registry.

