Vitamin K (doses, date/time)		X	
rFVIIa		X	
Fibrinogen (doses, date/time)		X	
Platelets units (number, date/time)		X	
Red Blood Cell (number, date/time)		X	
prothrombin complex concentrate		X	
Fresh frozen plasma (number, date/time)		X	
Imaging			
Type of Imaging		X	
CT or FAST positive for free fluid		X	
Outcome			
Date and time of death			X
Early death (<12 hours)	X	X	X
Early death (< 24h)			X
Massive Transfusion (defined by 10 RBC/24h)			X
Diagnosis			
Code AIS		X	
Final ISS		X	
Scores			
TASH Score	X	X	
ABC Score	X	X	
BATT Score	X	X	

Table 2. Summarize of potential baseline characteristics.

Age, mean (SD)
 
 - ≥ 65 years old, N (%) - < 65 years old, N (%) 
Sex male, N (%)
 
Mechanism of Injury: N (%)
 
 - Penetrating - Blunt 
Circumstances, N (%)
 
 - Road traffic Injury 
 ➤ Car ➤ Motorcycle ➤ Bicycle ➤ Pedestrian ➤ Other (train, boat) - Fall 
 ➤ > 3 meters ➤ < 3 meters ➤ Unclear - Gunshot - Stabbing - Explosion - Avalanche - Other - Unknown 
Physician staffed ambulance, N (%)
	
Prehospital SBP, mean (SD)
 
 - SBP < 90 mmHg, N (%) - SBP >90 mmHg, N, (%) 
Prehospital HR, mean (SD)
 
 - HR > 120/min, N (%) - HR < 120/min, N (%) 
Prehospital GCS, N (%)
 
 - 3-8 - 9-12 - 13-15 
Prehospital CPR, N (%)
 
ISS mean (SD)
 
ISS by categories, N (%)
 
 - 9-15 - 16-24 - 25-34 - ≥ 35 
Overall AIS score ≥3, N (%)
 
Severe head injury (AIS head ≥3), N (%)
	
ABC score, mean (SD)
 
0-1, N (%)
 
2-4, N (%)
 
TASH score, mean (SD)
 
 - 0-17, N (%) - 18-31, N (%) 
BATT score, mean (SD)
 
 - 0-7, N (%) - 8-12, N (%) 
Death due to bleeding, N (%)
 
Massive transfusion, N (%)
 
Early Death (<24h), N (%)
 
 - < 12h, N (%) - 12-24 h, N (%)

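### The first-hour red-cell rule reduces, but does not correct, the misclassification of patients who die of bleeding before reaching a transfusion threshold

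*SAP*

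**What the plan says.** SAP 4.4 names the problem: because "some patients will not survive long enough to receive 10 red blood cell units", it regards the massive transfusion outcome as misclassified in part. It then gives the remedy: "To correct this misclassification, the investigators add in the massive transfusion definition the use of" 3 or more units in the first hour, on the condition "if the variable is available in the registry".

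The primary outcome (SAP 5.1, item 6.1.1) is "defined by a transfusion equal to or greater than 10 Red blood cell (RBC) in the first 24 hours", or 3 or more units in the first hour if available. The protocol synopsis gives the same two-part definition. Death is not a component, and no composite, exclusion or competing-event rule covers patients who die first.

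The variable lists carry only the 24-hour threshold. The protocol has "Massive transfusion (defined as ≥ 10 red blood cells in the first 24 hours" and SAP Table 1 has "Massive Transfusion (defined by 10 RBC/24h". The protocol does, however, request the number of red-cell units in the first hour, and Table 1 requests red cells with date and time.

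Early death and death due to bleeding are separate secondary outcomes (item 6.2.2), analysed in the same way as the primary (5.2.1.1). The SAP discussion (section 6) contrasts BATT with an approach that finds "not only patients who have received a massive transfusion subject to survival bias".

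**The concern.** Massive transfusion is used here as a surrogate for haemorrhagic death. A patient who dies of bleeding before reaching either count is an event in spirit but a non-event in the data. A score that flags this patient is charged with a false positive.

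The plan's central aim is to compare TASH, ABC and BATT. If the scores differ in how strongly they flag rapidly fatal bleeding, the misclassification does not cancel in the comparison. TASH and ABC target massive transfusion; BATT targets death due to bleeding. That gives a reason to check whether the ranking depends on how these deaths are counted. The wording of SAP 4.4 tells the reader that no check is needed.

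**Working it through.** **Step 1. Read the definition.** No figure in the plan can be reproduced: there is no expected event rate or target AUROC, and 10,000 is an anticipated registry count. The logical check is enough for the main point. Among patients who die of bleeding:

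- 10 or more units in 24 hours: event.
- 3 or more units in hour one, fewer than 10 in total: event, but only if the first-hour variable is available.
- Fewer than 3 units in hour one and fewer than 10 in total: non-event. This includes patients who receive 3 to 9 units and die after the first hour.

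The rule rescues the second group and leaves the third. Without the first-hour variable, the second group is lost too and the whole stated problem remains.

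**Step 2. Direction and possible size (all inputs assumed except N).** Take N = 10,000 (SAP 3.2). Let M be patients with massive transfusion, E early haemorrhagic deaths below both thresholds, and C everyone else. Scores are normal with SD 1 and mean 0 in C, m in M and d in E. The AUROC between two groups with means a and b is Φ((a − b)/√2).

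- As planned (E are non-events): [C·AUC(M vs C) + E·AUC(M vs E)]/(C + E)
- With E as events: [M·AUC(M vs C) + E·AUC(E vs C)]/(M + E)

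Example: massive transfusion 5%, such deaths 1%, so M = 500, E = 100, C = 9,400.

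*Lethality-oriented score (m = 1.5, d = 2.5).* The three AUCs are Φ(1.061) = 0.856 (M vs C), Φ(−0.707) = 0.240 (M vs E) and Φ(1.768) = 0.961 (E vs C).
- As planned: (9,400 × 0.856 + 100 × 0.240)/9,500 = 0.849
- E as events: (500 × 0.856 + 100 × 0.961)/600 = 0.873

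*Transfusion-oriented score (m = d = 1.6).* AUC(M vs C) = 0.871 and AUC(M vs E) = 0.5.
- As planned: (9,400 × 0.871 + 100 × 0.5)/9,500 = 0.867
- E as events: 0.871

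At a cut-off of 1.3 (planned, then E as events):

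| Score | Sensitivity | Specificity | LR+ |
|---|---|---|---|
| Lethality-oriented | 0.579, 0.630 | 0.895, 0.903 | 5.51, 6.51 |
| Transfusion-oriented | 0.618, 0.618 | 0.898, 0.903 | 6.04, 6.38 |

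Sensitivity moves only where the early deaths score higher than other bleeders (d > m).

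**Step 3. Range.** AUROC of the lethality-oriented score with E as events:

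| Massive transfusion | Deaths 0.25% | 0.5% | 1% | 2% |
|---|---|---|---|---|
| 3% | 0.864 | 0.871 | 0.882 | 0.898 |
| 5% | 0.861 | 0.865 | 0.873 | 0.886 |
| 10% | 0.858 | 0.861 | 0.865 | 0.873 |

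Its planned values run from 0.854 (0.25% deaths) to about 0.843 (2%), so the loss is 0.004 to 0.055. The transfusion-oriented score has 0.871 throughout with E as events and 0.870 to 0.863 as planned, a loss of 0.001 to 0.008. As planned, it ranks first in every cell. With E as events the order reverses at 1% and 2% deaths when massive transfusion is 3% or 5%, and only at 2% when it is 10%. At 0.25% there is no reversal.

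**Step 4. Boundary.** The direction depends on these patients scoring high. If they scored like non-bleeders (d = 0), the transfusion-oriented score would lose nothing as planned (0.871), and counting them as events would lower its AUROC to (500 × 0.871 + 100 × 0.5)/600 = 0.809.

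**The case against.** The SAP is open about the limitation, in 4.4 and again in section 6. It pre-specifies early death and death due to bleeding as secondary outcomes, repeats the full analysis on them, and supplies a proxy if cause of death is missing. All three scores will therefore be judged on lethal bleeding. The exclusion of patients who arrive without signs of life and for whom nothing was started also removes part of the affected group. This stands as mitigation and limits the gain from a further analysis. It does not change how these patients are counted in the primary comparison, and it does not make *correct* the right word.

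A reader might go further and infer that BATT is penalised more than TASH and ABC, so that the head-to-head result is distorted. The documents do not support that. They list the items of TASH and ABC but not those of BATT, so nothing shows that BATT ranks rapid deaths above TASH, which weights haemoglobin, base excess and blood pressure. In the calculation above, the larger loss and the reversal follow from the assumed d = 2.5.

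A reader might also infer that sensitivity and specificity are both materially biased downward. Specificity moves by less than one percentage point in the worked example, and sensitivity is unchanged unless the early deaths outscore other bleeders.

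Finally, the variable lists might suggest that the first-hour rule has been dropped. Both outcome definitions still contain it.

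**Conclusion.** The point holds in a limited form. From the definition alone, the first-hour rule reduces the misclassification and does not correct it, and if the variable is missing nothing is reduced. That conclusion needs no assumption.

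The effect on performance is conditional. If these patients score high, AUROC and LR+ fall and specificity falls slightly. The ranges in the working are illustrations built on assumed prevalence, death rates and score separations; none comes from the documents. A larger loss for BATT is possible, given its target outcome, but not shown. Whether the ranking could change depends largely on how many patients die below both thresholds, a count that the SAP does not plan to report.

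**What to change.** Keep the primary outcome and make four changes before the dataset is received:

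1. In SAP 4.4, say that the first-hour rule is meant to *reduce* the misclassification.
2. Report the number of deaths within 24 hours below both red-cell thresholds.
3. Pre-specify one sensitivity analysis in which the event is massive transfusion or death within 24 hours with evidence of haemorrhage. Apply the evidence-of-bleeding criteria in SAP 5.2.2 (under Missing Data) to all deaths within 24 hours. The proxy there cannot be used as it stands: it requires such evidence only for deaths at 12 to 24 hours and takes deaths within 12 hours from almost any cause. In a cohort that admits patients on AIS head ≥ 3 alone, that would add non-haemorrhagic deaths.
4. State whether the ranking of the scores changes.

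The cost is one derived outcome and one table. Time of death, red-cell times and AIS codes are already requested. Activation of a massive transfusion protocol, one of the listed criteria, is not in Table 1; it would have to be requested as a complementary variable or left out. The drawback is a mixed endpoint that contains BATT's own target and may favour BATT. It should therefore stay a sensitivity analysis, read beside the unchanged primary and the separate death outcomes.
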